- The most knowledgeable respondent is not always available. Enumerators are given instructions on who within the facility should respond to each questionnaire. However, the most appropriate respondent is not always available (due to illness, leave, other obligations, etc.) and the enumerator will have to interview the next most appropriate respondent who may not have as much knowledge of the topic. For example, if the person who manages the stock room is not available, their assistant may have to respond to the questionnaire.
- Some comparisons across time are not possible because of changes in the data collection tools. Data collection tools were refined after Phase I, Round 1 data collection to facilitate better respondent understanding, to add more color to the questions being asked, to streamline the data collection process, or to probe further into questions that came up in Phase I, Round 1. In some cases, these changes might mean that variables are measured differently between rounds, which may prohibit direct comparisons across rounds.
- Differences across rounds may reflect different respondents rather than true change. In some cases, respondents in Phase II may be different than those in previous rounds. Thus, differences in responses may reflect different levels of knowledge across respondents rather than change over time.

Ethical Considerations

I. Risks

This study poses limited risk to study participants. There is no risk involved in surveying public healthcare facilities or other study components for either the enumerators or the facility staff. Facility staff's regular workload and compensation is unlikely to be affected. Some survey activities may briefly stop healthcare

workers from performing their duties, but it will be stated clearly that workers are free to stop or pause at any time (such as in a medical emergency).

II. Benefits

This study contributes to the understanding of the availability and stocking of pneumonia treatments in Tanzania. Findings will benefit public and private health facilities, the Tanzanian government, and medical distributors by providing information that can improve treatment of pneumonia in Tanzania. Ultimately, the study will benefit Tanzanian children with pneumonia by improving available treatment.

III. Informed Consent

All healthcare workers will be read an informed consent form prior to the interview. The informed consent form will emphasize that participation is completely voluntary. Participants will not be provided any compensation.

An important point to note with regards to consent is that we are planning on including a more generalized study title in written information and consent forms to blind study participants and mitigate Hawthorne effects. The study title listed on the consent and written information forms will be “Monitoring and Evaluating the Availability, Stocking and Dispensing of Childhood Illness Treatments in Public and Private Sector Markets in Tanzania”.

IV. Data Management and Confidentiality

Risks involving data management and data security are minimal. Trained enumerators will use smart phones and tablets to collect all data. Electronic questionnaires will be encrypted with a password. We will use Stata (version 14) to analyze the data. Primary data analysis will include quality control checks, such as checks for missing data and data entry.

Results Sharing

Any publication of study results will be decided among investigators before submitting results for publication. Results from each round of data collection will be disseminated annually, alongside any salient updates on research plans, with the relevant MoHCDGEC departments, e.g. RCHS, prevention and policy, etc. and other bodies that could benefit from the data, such as the Medical Stores Department and the Pharmacy Council. The final list of stakeholders to be invited for dissemination will be decided upon in collaboration with the MoHCDGEC. The presentation may take the form of in-person presentations to key stakeholders at the leadership level of the MoHCDGEC, MSD, and TFDA.

These annual disseminations at the national government level could be complemented with disseminations at the local level, where results could be shared among key decision makers, such as district medical officers, and regional medical officers. This may be done through sharing a brief report on the results accompanied by any salient updates on research plans as well as a list of best practices and key takeaways from the study in regard to childhood pneumonia case management. Similar to the national

level dissemination, the final list of local level stakeholders would be decided upon in collaboration with the MoHCDGEC.

The policy implications of this study are potentially twofold:

1. Short-term policy implications: These policies can result from the first few rounds of data collection and results sharing. One potential outcome could be a new policy that targets the strengthening of public supply chains for facilities with frequent pneumonia treatment shortages.
2. Long-term policy implications: After the dissemination of results following the final round of data collection in December 2021, R4D hopes to help with shaping new policies and approaches to pneumonia case management in children in Tanzania. By shedding light on a childhood illness that does not attract sufficient funding from donors and NGOs as compared to other illnesses, this case study could assist the MoHCDGEC in securing funding and programs that continue to target childhood pneumonia.

In addition to disseminating the findings of this research with key stakeholders in Tanzania, R4D will also share the findings with GiveWell. R4D will consult with its GoT partners prior to the findings being made public on GiveWell's website.

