antibiotics. As a result, WHO revised its guidelines in 2011 to recommend amoxicillin over co-trimoxazole. In 2013, UNICEF began supporting dispersible tablets over oral suspension as the recommended formulation of amoxicillin for children under five since they are easier to dose and administer to children, have a longer shelf life, are cheaper, and offer supply chain advantages due to lower volume and weight (UNICEF, 2013).

² In a CATI survey, an enumerator collects information from respondents by calling them on the phone and recording their answers on a tablet.

The primary aim of Phase II³ is to:

Estimate availability⁴ and stocking⁵ levels of pediatric amoxicillin⁶ (peds-Amox) in the public health facilities

The secondary aim⁷ is to:

Estimate and identify availability and stocking levels of other childhood illness treatments. In particular, we will focus on the availability and stocking of cotrimoxazole oral suspension (cotrim OS) – a broad spectrum antibiotic that is often used as an alternative treatment for non-severe pneumonia – artemether lumefantrine (ALU)/Coartem, Zinc/ORS co-pack, Gentamycin, ferrous sulphate/folic acid (FeFol), Benzylpenicillin injection (penicillin G/Chrystapen), and paracetamol

Research Methodology

This round of surveying is intended to capture changes in Amox-DT availability and stocking as a result of the first three years of R4D’s partnership with GoT to facilitate Amox-DT importation and distribution across Tanzania. However, since some R4D-funded Amox-DT had already been distributed to health facilities during the initial round of data collection (Phase I, Round 1), a true baseline could not be established. Consequently, any differences measured between baseline and this round of data collection may underestimate R4D’s influence on Amox-DT availability and stocking.

³ The in-person round includes one additional primary aim: Assess provider knowledge of pneumonia diagnosis and prescription protocols. This primary aim is excluded from the remote round primary aims as no interview is conducted with a health care provider in the remote rounds. This is because, as referenced above, the remote survey instrument is shorter; it is also focused on one primary respondent: the stock room attendant.

⁴ Availability is a binary variable reflecting the presence of one or more units of a medicine in a facility versus zero units.

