⁵ Stocking is defined as whether there has been a stockout in the 90 days prior to the facility visit by the survey team.

⁶ Pediatric amoxicillin refers to the two primary pediatric formulations of amoxicillin that are intended for use with children under five, Amox-DT and amoxicillin oral suspension/syrup (Amox-OS)

⁷ The in-person round includes an additional secondary aim: Assess how providers alter prescription behavior when faced with a peds-Amox stock out. As described in the footnote above, no interview is conducted with health care providers in the remote rounds.

I. Research Questions & Indicators

The goal is to monitor whether Amox-DT, and peds-Amox more broadly, are reaching health facilities and being dispensed to children appropriately. The four main research questions that guide Phase II are⁸:

1. What is the availability of peds-Amox in public health facilities?
2. Has the availability of peds-Amox in public health facilities changed over the past three years? If so, by how much?
3. What are the stocking levels of peds-Amox in public health facilities?
4. Has the stocking of peds-Amox in public health facilities changed over the past three years? If so, by how much?

The primary and secondary outcomes from the survey used to explore each of these questions are presented in the Outcomes section, in *Table 1*.

II. Sampling Method

Phase I

Prior to Phase I, R4D worked with the MoHCDGEC to obtain a list of all public health facilities in Tanzania at three levels: district hospitals, health centers and dispensaries. Using this list, we implemented a stratified two-stage sampling method to select a nationally representative sample of public health facilities across the 26 mainland regions of Tanzania to be included in the baseline and subsequent rounds of data collection. The sampling process is outlined below.

1. Randomly selected three districts from each of the 26 regions of mainland Tanzania^{9,10,11}
2. Randomly selected facilities based on the category of facility from each council:
 - One district hospital was selected per district (if available)¹²
 - One health center was selected per district (if available)
 - Seven dispensaries were selected per district¹³

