3. Purposively selected the Dar es Salaam and Mwanza regions to ensure population and urban representation, resulting a total of 10 regions selected.

In the 2017 study, there were an average of 25 facilities sampled per region, across three districts. All facilities from the 2017 Phase I sample in these ten regions were included in our Phase II sample, resulting in a sample size of 251 health facilities. This approach will allow outcomes to be compared over time within each facility from 2017 to 2021 and allows to detect a change of 8.51 percentage points.

If a facility is permanently closed over the course of Phase II data collection, a facility of the same category (district hospital, health center, dispensary) will be randomly selected from the same district to serve as a replacement facility in the sample.

III. Data Collection

Round 1 of Phase I was conducted in March 2017,¹⁵ Round 2 was conducted in July 2017, and Round 3 was conducted November 2017.

Data collection for the first remote round of Phase II will be conducted over 3 weeks from May 12, 2020 to June 8, 2020.

Data collection methods

The remote public health facility survey employs a CATI data collection method in which enumerators speak with respondents over the phone and record responses in a tablet as the responses are given. The

¹⁴ Geopolitical zones were defined as those used in the 2015/2016 Demographic and Health Survey (DHS) and 2017 Malaria Indicator Survey.

¹⁵ The first round of data collection in March 2017 was intended to serve as a baseline measure of Amox-DT availability, stocking, and dispensing before R4D-funded Amox-DT reached health facilities. However, since peds-Amox had already reached emergency stocking levels nation-wide, R4D and the MoHCDGEC agreed to start Amox-DT distribution upon its arrival in country in late 2016. The first shipment of R4D-administered Amox-DT reached MSD zonal stores on January 15, 2017 and began distribution to health facilities shortly thereafter.

survey is a structured interview that includes requests for respondents to conduct stock counts and carry out record reviews.

The survey is comprised of three questionnaires:

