- **Training oversight:** During the five-day enumerator training, an R4D Senior Project Officer and Senior Program Associate were present to answer questions and provide explanations about the protocols.
- **Electronic data collection:** Electronic data collection allows for automated skip patterns and built-in consistency checks to identify errors and missing values during the interview, allowing enumerators to correct their submissions while still at the facility.
- **Field review:** Before data is transmitted to the EDI headquarters, a supervisor checks each survey completed by enumerators for possible errors and areas needing clarification with the facility.
- **EDI consistency checks:** The EDI Data Processing Officer and Team Leader perform a range of checks on incoming data throughout data collection to check for inconsistencies and errors across field teams.
- **Call observations (spot checks):** EDI supervisors dial in to listen to a subsample of interviews – one per enumerator per questionnaire – and complete observation checklists. Observations serve as an opportunity to provide feedback on data collection, enforce best practices in data collection, and send generalizable notes to the full survey team.
- **Survey back-checks:** EDI created an abbreviated version of the original questionnaires for re-interviews in a subset of public health facilities. The responses from re-interviews are compared to the original responses. Re-interviews occur in a representative sample in terms of region, facility type, and questionnaire, and are completed for 20% of interviews per enumerator.
- **Facility follow-up during data cleaning:** When the EDI data processing team finds errors or inconsistencies during data cleaning, the team contacts the corresponding enumerator or respondent on the phone to clarify the response and update the interview file.

Analysis

I. Summary Statistics

First, we will present summary statistics of key metrics for outcomes related to availability and stocking of peds-Amox. This will allow us to compare changes in our metrics of interest over time. Summary statistics for health facilities in Phase II will be visualized in comparison with Phase I, Rounds 1-3 values of the same outcomes.

Summary statistics will further be disaggregated as applicable by:

- Amoxicillin type (Amox-DT, Amox-OS, and peds-Amox)
- Health facility type
- Integrated Logistics System (ILS) subgroup
- Region
- MSD zone

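### The plan names only under-estimation as the bias from its Phase I Round 1 reference, but its own footnote gives a reason for over-estimation; the net direction is unknown and the round coefficient should not be labelled a programme effect

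*Combined protocol and SAP*

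**What the plan says.** - **Direction of bias.** Research Methodology says that "a true baseline could not be established" because some programme-funded product was already in facilities at Phase I Round 1. It concludes that "any differences measured between baseline and this round of data collection may underestimate" the programme's influence, for availability and stocking alike. No other direction is mentioned there.
- **State of supply.** Footnote 15 (III. Data Collection) explains why distribution was not held back for a baseline: "peds-Amox had already reached emergency stocking levels nation-wide". It adds that "The first shipment of R4D-administered Amox-DT reached MSD zonal stores on January 15, 2017", with distribution to facilities shortly afterwards.
- **Timing and look-back.** "Round 1 of Phase I was conducted in March 2017". Footnote 5: "Stocking is defined as whether there has been a stockout in the 90 days prior". Table 1 counts one day without stock as a stock-out.
- **Models.** Eq 3a and 4a use Phase I Round 1 as the only reference. Eq 4a contains only the round indicator, and Eq 3a adds facility category. Both specifications say beta_1 will report the mean effect of three or more years of catalytic funding.
- **Caveats.** Changes over Time says causality cannot be stated definitively and that other factors may act in both directions. It then says that covariates, fixed effects, clustering and robustness checks allow the programme's effect to be estimated.
- **Rounds 2 and 3.** Summary statistics will be "visualized in comparison with Phase I, Rounds 1-3 values of the same outcomes". No regression uses these rounds as the reference.

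**The concern.** A before-and-after change is only as interpretable as its starting point. The plan tells readers that its starting point is, if anything, too high. Its footnote reports that the level just before the programme was an emergency low. A low that would have corrected itself in part makes the later change look larger than the programme's contribution. A reader who sees only the under-estimation statement may treat the reported change as conservative, and the label on beta_1 encourages that reading. What is at stake is how much of any change in the two primary outcomes may be credited to the funding.

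**Working it through.** **1. Dates (footnotes 5 and 15, III. Data Collection).** For interviews throughout March 2017:

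| Interview | 90-day window opens | Days in window before January 15, 2017 | Days from January 15 to interview |
|---|---|---|---|
| March 1, 2017 | December 1, 2016 | 45 | 45 |
| March 31, 2017 | December 31, 2016 | 15 | 75 |

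So 15 to 45 of the 90 days precede arrival at the zonal stores. Facilities received stock later still, so these are minimum counts of days without programme stock at a facility. Programme stock cannot undo a stock-out day that had already happened, and one such day is enough to score the outcome. The under-estimation mechanism is therefore weaker for stock-outs than for availability. Availability is measured on the survey day, 45 to 75 days after the zonal arrival, and nothing in the documents says what its level then was.

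**2. Direction of bias.** For availability, let P be the full programme effect, c the early programme gain already present at Round 1, and r the recovery that would have occurred without the programme. Then

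change since Round 1 = P + r − c, so bias as an estimate of P = r − c.

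The documents give neither r nor c. With assumed values in percentage points:

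- r = 5, c = 10: bias −5
- r = 5, c = 5: bias 0
- r = 10, c = 5: bias +5

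The plan discusses only c. For stock-outs the signs reverse, because improvement is a negative beta_1.

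**3. Can the models remove r?** A recovery common to all facilities takes one value at Round 1 and another at the Phase II round, so it is collinear with the round indicator. Category, facility, region and strata fixed effects do not vary over time and cannot absorb it. Clustering changes only the standard error. The one time-varying proxy for system supply, mean availability of all surveyed medicines, enters only the robustness models (Eq 3c, 4c). As worded it appears to include the outcome medicine, and the other medicines in it would not capture a shortage specific to amoxicillin.

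**4. The plan's one design figure.** II. Sampling Method gives a detectable change of 8.51 points with 251 facilities. It cannot be reproduced, because power, sidedness, baseline rate, within-facility correlation and design effect are not stated. It is attainable: at two-sided 0.05 and 80% power, a paired design needs a standard deviation of the difference of 0.0851 × √251 / 2.802 = 0.481. The plan does not say which outcome it refers to.

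**5. Illustration only.** Assume 8.51 points means 80% power at two-sided 0.05, so SE = 8.51 / 2.802 = 3.04 points, and assume P = 0 and c = 0. The chance of a significant rise in availability is Φ(r / 3.04 − 1.96):

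| Assumed r (points) | Chance of a significant rise |
|---|---|
| 0 | 2.5% |
| 2 | 9.7% |
| 5 | 37.7% |
| 8.51 | 80% |
| 10 | 90.9% |

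At a first Holm step of 0.05/3 (three availability metrics in Table 1), r = 5 gives 22.7% and r = 10 gives 81.5%. Multiplicity correction does not deal with this kind of error. The table shows sensitivity to r and is not an estimate of r.

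**The case against.** The strongest reply has four parts.

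**The plan is already cautious.** It says may underestimate, its mechanism is real, it disclaims a definitive causal reading, and it allows for influences in both directions. It tracks comparator medicines, shows Rounds 2 and 3 descriptively, and promises weighted Phase I means with 95% confidence intervals, not restricted to Round 1. This stands, and it makes the statement incomplete, not wrong. But the safeguards are partial: none names the emergency, none is a primary adjustment, and the label on beta_1 contradicts the disclaimer.

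**Round 1 may not have been in the trough.** A reader might infer that the baseline was taken during the emergency. Footnote 15 does not say so. It describes the situation when early distribution was agreed, and product had been moving for some weeks by March 2017. This stands for same-day availability.

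**Recovery without the programme is assumed.** No section says supply would have recovered unaided. If programme stock ended the shortage, that recovery is programme effect. This stands, and is why the sign is open.

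**Pre-shipment days suit a baseline.** Round 1 was meant to precede programme stock, so days before January 15 bring the stock-out window closer to that intention. That is correct. They lead to over-estimation only if the shortage would have eased anyway. They also undercut the claim that under-estimation applies equally to stocking.

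**Conclusion.** The concern holds as a matter of incomplete reasoning and over-labelling. The plan states one direction of bias, while its own footnote gives grounds for the other. Its primary models cannot tell recovery from programme effect, yet the coefficient is called a mean effect.

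The only quantity the documents fix is the overlap: 15 to 45 of 90 days for the stock-out outcome, taking interviews as spread over March 1 to 31, 2017. The net bias is r − c, with both terms unknown, so no size or sign can be given. A reader might conclude that the result is an upper bound, or that the under-estimation statement is false. The documents support neither. Nor do they support treating the result as a lower bound, which the plan itself does not claim.

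**What to change.** 1. **Research Methodology.** Say that bias from using Phase I Round 1 may run in either direction: downward because programme stock was already in facilities, upward because supply had been at an emergency low before distribution. Add that the Round 1 stock-out window includes days before the first shipment.
2. **Changes over Time and both specifications.** Describe beta_1 as the change since Phase I Round 1 (adjusted for facility category in Eq 3a), not as the mean effect of catalytic funding. Drop the claim that fixed effects and clustering allow the programme's effect to be estimated.
3. **Sensitivity contrasts.** For the two primary outcomes, pre-specify Eq 3a and 4a for each Phase II round against Phase I Round 2 (July 2017) and Round 3 (November 2017), outside the Holm families. Their 90-day windows open no earlier than April 2 and August 3, 2017, clear of the pre-shipment period. Present them as showing how far the change depends on the reference round. State that both rounds are post-distribution and so omit early programme gains. They do not bracket the programme effect, and agreement in sign would not establish one, since a shared trend would also produce it.

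The cost is a few sentences and one extra table from Phase I data already collected. The plan says it was drafted before any Phase II data were analysed, so the contrasts can be pre-specified if they are added before that analysis. The downside is that the later-reference estimates may look less favourable.
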